**Table 9 Timeframes for submitting serious adverse event and other events reports to GSK Biologicals**

Type of Event	Initial Reports		Follow-up of Relevant Information on a Previous Report	
	Timeframe	Documents	Timeframe	Documents
SAEs/pIMDs	24 hours*‡	Electronic Expedited Adverse Events Report	24 hours*	Electronic Expedited Adverse Events Report

\*Timeframe allowed after receipt or awareness of the information.

‡The investigator will be required to confirm review of the SAE/pIMD causality by ticking the 'reviewed' box in the electronic Expedited Adverse Events Report within 72 hours of submission of the SAE/pIMDs.

**CONFIDENTIAL**204913 (NTHI-MCAT-006 EXT:001)  
Protocol Amendment 1 Final**8.3.2. Contact information for reporting serious adverse events and pIMDs**

Study Contact for Reporting SAEs and pIMDs
Refer to the local study contact information document.
Back-up Study Contact for Reporting SAEs and pIMDs
24/24 hour and 7/7 day availability:

**8.3.3. Completion and transmission of SAE reports to GSK Biologicals**

Once an investigator becomes aware that a SAE has occurred in a study subject, the investigator (or designate) must complete the information in the electronic Expedited Adverse Events Report **WITHIN 24 HOURS**. The report will always be completed as thoroughly as possible with all available details of the event. Even if the investigator does not have all information regarding a SAE, the report should still be completed within 24 hours. Once additional relevant information is received, the report should be updated **WITHIN 24 HOURS**.

The investigator will always provide an assessment of causality at the time of the initial report. The investigator will be required to confirm the review of the SAE causality by ticking the 'reviewed' box in the electronic Expedited Adverse Events Report within 72 hours of submission of the SAE.

**8.3.3.1. Back-up system in case the electronic reporting system does not work**

If the electronic reporting system does not work, the investigator (or designate) must complete, then date and sign a paper Expedited Adverse Events Report and fax it to the Study Contact for Reporting SAEs (refer to the [Sponsor Information](#)) or to GSK Biologicals Clinical Safety and Pharmacovigilance department within 24 hours.

This back-up system should only be used if the electronic reporting system is not working and NOT if the system is slow. As soon as the electronic reporting system is working again, the investigator (or designate) must complete the electronic Expedited Adverse Events Report within 24 hours. The final valid information for regulatory reporting will be the information reported through the electronic SAE reporting system.

**CONFIDENTIAL**204913 (NTHI-MCAT-006 EXT:001)  
Protocol Amendment 1 Final

### **8.3.4. Reporting of pIMDs to GSK Biologicals**

Once a pIMD is diagnosed (serious or non-serious) in a study subject, the investigator (or designate) must complete the information in the electronic Expedited Adverse Events Report **WITHIN 24 HOURS** after he/she becomes aware of the diagnosis. The report allows to specify that the event is a pIMD and whether it is serious or non-serious. The report will always be completed as thoroughly as possible with all available details of the event, in accordance with the pIMD standard questionnaire provided. Even if the investigator does not have all information regarding a pIMD, the report should still be completed within 24 hours. Once additional relevant information is received, the report should be updated **WITHIN 24 HOURS**.

The investigator will always provide an assessment of causality at the time of the initial report. The investigator will be required to confirm the review of the pIMD causality by ticking the 'reviewed' box in the electronic Expedited Adverse Events Report within 72 hours of submission of the pIMD.

Refer to Section [8.3.3.1](#) for back-up system in case the electronic reporting system does not work.

### **8.3.5. Updating of SAE and pIMD information after removal of write access to the subject's eCRF**

When additional SAE or pIMD information is received after removal of the write access to the subject's eCRF, new or updated information should be recorded on the appropriate paper report, with all changes signed and dated by the investigator. The updated report should be faxed to the Study Contact for Reporting SAEs (refer to the [Sponsor Information](#)) or to GSK Biologicals Clinical Safety and Pharmacovigilance department within the designated reporting time frames specified in [Table 9](#).

### **8.3.6. Regulatory reporting requirements for serious adverse events**

The investigator will promptly report all SAEs to GSK in accordance with the procedures detailed in Section [8.3.1](#). GSK Biologicals has a legal responsibility to promptly notify, as appropriate, both the local regulatory authority and other regulatory agencies about the safety of a product under clinical investigation. Prompt notification of SAEs by the investigator to the Study Contact for Reporting SAEs is essential so that legal obligations and ethical responsibilities towards the safety of other subjects are met.

Investigator safety reports are prepared according to the current GSK policy and are forwarded to investigators as necessary. An investigator safety report is prepared for a SAE(s) that is both attributable to the study vaccine(s) and unexpected. The purpose of the report is to fulfil specific regulatory and GCP requirements, regarding the product under investigation.

**CONFIDENTIAL**204913 (NTHI-MCAT-006 EXT:001)  
Protocol Amendment 1 Final**8.4. Follow-up of serious adverse events****8.4.1. Follow-up of serious adverse events****8.4.1.1. Follow-up during the study**

After the initial SAE report, the investigator is required to proactively follow each subject and provide additional relevant information on the subject's condition to GSK Biologicals (within 24 hours for SAEs; refer to [Table 9](#)).

All SAEs and pIMDs (serious or non-serious) documented at a previous visit/contact and designated as not recovered/not resolved or recovering/resolving will be reviewed at subsequent visits/contacts until the last visit of the subject.

**8.4.1.2. Follow-up after the subject is discharged from the study**

The investigator will follow subjects:

- with SAEs, pIMDs (serious or non-serious), or subjects withdrawn from the study as a result of an AE, until the event has resolved, subsided, stabilised, disappeared, or until the event is otherwise explained, or the subject is lost to follow-up.

If the investigator receives additional relevant information on a previously reported SAE, he/she will provide this information to GSK Biologicals using a paper/ electronic Expedited Adverse Events Report as applicable.

If the study is concluded, the investigator should send the information via email to safety (Email address: [PPD](#) ) using SAE paper form.

GSK Biologicals may request that the investigator performs or arranges the conduct of additional clinical examinations/tests and/or evaluations to elucidate as fully as possible the nature and/or causality of the SAE. The investigator is obliged to assist. If a subject dies during participation in the study or during a recognised follow-up period, GSK Biologicals will be provided with any available post-mortem findings, including histopathology.

**8.5. Treatment of serious adverse events**

Treatment of any SAE is at the sole discretion of the investigator and according to current good medical practice. Any medication administered for the treatment of a SAE / pIMD should be recorded in Expedited Adverse Event Report of the subject's eCRF (refer to [Section 6.1](#)).

**CONFIDENTIAL**204913 (NTHI-MCAT-006 EXT:001)  
Protocol Amendment 1 Final

## **8.6. Subject card**

Study subjects/LAR(s) must be provided with the address and telephone number of the main contact for information about the clinical study.

The investigator (or designate) must therefore provide a “subject card” to each subject/LAR(s). In an emergency situation this card serves to inform the responsible attending physician that the subject is in a clinical study and that relevant information may be obtained by contacting the investigator.

Subjects/LAR(s) must be instructed to keep subject cards in their possession at all times during the study duration.

## **9. SUBJECT COMPLETION AND WITHDRAWAL**

### **9.1. Subject completion**

A subject who returns for the concluding visit foreseen in the protocol is considered to have completed the study.

### **9.2. Subject withdrawal**

Withdrawals will not be replaced.

#### **9.2.1. Subject withdrawal from the study**

From an analysis perspective, a ‘withdrawal’ from the study refers to any subject who did not come back for the concluding visit foreseen in the protocol.

All data collected until the date of withdrawal/last contact of the subject will be used for the analysis.

A subject is considered a ‘withdrawal’ from the study when no study procedure has occurred, no follow-up has been performed and no further information has been collected for this subject from the date of withdrawal/last contact.

Investigators will make at least 3 attempts (e.g. 3 telephone calls) to contact those subjects who do not return for scheduled visits or follow-up.

Information relative to the withdrawal will be documented in the eCRF. The investigator will document whether the decision to withdraw a subject from the study was made by the subject himself/herself, by the subject’s LAR(s), or by the investigator, as well as which of the following possible reasons was responsible for withdrawal:

- Serious adverse event.
- Protocol violation (specify).

**CONFIDENTIAL**204913 (NTHI-MCAT-006 EXT:001)  
Protocol Amendment 1 Final

- Consent withdrawal, not due to a serious adverse event\*.
- Moved from the study area.
- Lost to follow-up.
- Other (specify).

\*In case a subject is withdrawn from the study because he/she/the subject's LAR(s) has withdrawn consent, the investigator will document the reason for withdrawal of consent, if specified by the subject/subject's LAR(s), in the eCRF.

Subjects who are withdrawn from the study because of SAEs must be clearly distinguished from subjects who are withdrawn for other reasons. Investigators will follow subjects who are withdrawn from the study as result of a SAE until resolution of the event (see Section [8.4.1.2](#)).

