## 2.2. Secondary objective

- To assess the safety of the investigational NTHi-Mcat vaccine in terms of serious adverse events and potential immune-mediated diseases up to 3 years after the last planned visit (Month 14) in the NTHi-Mcat-001 study.

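### Protocol section 9.2.1 has no status that keeps a subject who can no longer attend site visits in SAE/pIMD follow-up, and the SAP then counts that subject as event-free

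*Protocol*

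**What the plan says.** The secondary objective (Protocol 2.2) is safety in terms of SAEs and pIMDs, "up to 3 years after the last planned visit (Month 14) in the NTHi-Mcat-001 study". No vaccine is given in this study. Each of the six contacts in Protocol Table 2 (Months 20, 26, 32, 38, 44 and 50) is a numbered visit that combines a blood draw of about 20 mL with the recording of SAEs and pIMDs.

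Protocol 9.1 defines completion: "A subject who returns for the concluding visit foreseen in the protocol is considered to have completed the study". Protocol 9.2.1 then describes a withdrawal in two ways:

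- For analysis, the term "refers to any subject who did not come back for the concluding visit foreseen in the protocol".
- A second definition requires the absence of any further procedure and adds two conditions: "no follow-up has been performed and no further information has been collected for this subject from the date of withdrawal/last contact".

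The listed reasons include "Moved from the study area". Subjects who do not return get at least three contact attempts, for example by telephone. The section does not say that SAEs, pIMDs or vital status should be asked about or recorded when an attempt succeeds.

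Some follow-up does survive withdrawal. Section 9.2.1 states: "Investigators will follow subjects who are withdrawn from the study as result of a SAE until resolution of the event". Section 8.4.1.2 extends follow-up after discharge to existing SAEs and pIMDs, and section 8.2.1 requires SAEs that lead to withdrawal to be recorded. For new events after discharge, section 8.2.2 imposes no duty to search. An SAE is notified only if the investigator happens to learn of it and considers it related to the vaccine.

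SAP 11.2.4 uses all enrolled subjects as the denominator for SAEs and pIMDs, and treats anyone without a report as not having had the event.

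**The concern.** A blood sample needs attendance, but an SAE or pIMD report does not. Detection rests on a non-leading question and review of medical documents (Protocol 8.2.3.1), both of which can be done at a distance. A subject who moves away can no longer serve the primary objective but could still serve the secondary one. The protocol gives sites no status for that subject other than withdrawal, after which planned detection of new events ends.

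The SAP turns this missing follow-up into an apparent absence of events. A subject who leaves at Month 26 and develops a pIMD at Month 40 appears in the final table as a subject observed without a pIMD. The percentages for the only secondary objective are then biased downward, and their exact confidence intervals do not widen to reflect the lost time. Protocol 1.2.1 says pIMDs will be closely monitored because the vaccine was adjuvanted, so avoidable loss here deserves attention.

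**Working it through.** **Text check: a subject who moves away after Visit 2 with no known SAE or pIMD**

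1. No remaining planned contact can be met, because all are site visits (Table 2).
2. The reason recorded is relocation, and the only status available is withdrawal (9.2.1).
3. The provisions that survive withdrawal do not apply: there is no existing event (8.4.1.2), no SAE behind the withdrawal (8.2.1, 9.2.1) and no documented event to be "reviewed at subsequent visits/contacts until the last visit of the subject" (8.4.1.1).
4. A later SAE reaches the sponsor only if the investigator learns of it and judges it vaccine-related. Section 8.2.2 gives no route for a new non-serious pIMD.
5. SAP 11.2.4 counts the subject as event-free, in a denominator of all enrolled subjects.

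**Text check: the two definitions.** A subject misses Visit 6 but answers SAE/pIMD questions by telephone at Month 50. By the first definition this is a withdrawal, because the concluding visit was missed. By the second it is not, because further information was collected. By section 9.1 the subject has not completed. SAP 6.1.1 tabulates withdrawals by reason, so the disposition table depends on which definition is used.

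**Size.** The documents give no dropout rate and compute no sample size (Protocol 10.3), so there is no figure of the plan's own to reproduce. What follows is illustration under stated assumptions.

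*Follow-up lost.* If all 90 subjects enrol for 30 months, the total is 90 × 30 = 2,700 person-months. With a share p leaving at mid-study on average, the loss is 0.5 × p × 2,700, which is 135 person-months at p = 0.10 and 270 at p = 0.20.

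*Share of events missed.* Let leavers have RR times the event rate of others throughout, and lose half their follow-up:

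missed share = 0.5 × p × RR / [(1 − p) + p × RR]

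| RR | p = 0.10 | p = 0.20 |
|---|---|---|
| 1 | 0.05/1.00 = 5% | 0.10/1.00 = 10% |
| 2 | 0.10/1.10 = 9% | 0.20/1.20 = 17% |
| 3 | 0.15/1.20 = 13% | 0.30/1.40 = 21% |

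*Effect on a reported percentage.* Assume RR = 1, a constant hazard and withdrawal uniform over 30 months. With true 30-month proportion q and h = −ln(1 − q), a leaver's chance of an event before leaving is 1 − q/h. For q = 0.20, h = 0.223 and this chance is 0.104. The expected observed proportion is (1 − p) × 0.20 + p × 0.104, which is 19.0% at p = 0.10 and 18.1% at p = 0.20. In a group of 30 the true expectation is 6.0 subjects, and the observed expectation is 5.7 or 5.4.

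*Zero events.* The Clopper-Pearson upper 95% limit for 0/30 is 11.6%, and SAP 11.2.4 would print that limit whatever the dropout. If leavers were treated as contributing nothing, which is an extreme, the limit would be 12.8% with 27 subjects and 14.2% with 24.

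**The case against.** A reader might infer that section 9.2.1 makes every withdrawal total. The documents do not support that. The sentence containing "no follow-up has been performed and no further information has been collected for this subject from the date of withdrawal/last contact" states a joint condition for classifying a subject after the fact. It does not order collection to stop, and a subject still giving safety information would not meet it. Nor is the loss of follow-up universal, given the provisions in 8.2.1, 8.4.1.2 and 9.2.1 already described.

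A reader might also infer that a subject who only refuses blood draws must leave. No passage says so. Completion requires return for the concluding visit, not a sample. An unperformed sample leads to SAP elimination code 2100, which affects the Per-Protocol Set, while the Exposed Set for safety contains all enrolled subjects. Likewise, forbidden medication explicitly does not require withdrawal (Protocol 6.1.2), and mistimed samples lead to Per-Protocol exclusion (SAP code 2090). Protocol violation is a reason to record if withdrawal happens, not a rule that it must happen.

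The argument that leavers are sicker is weakened too. An SAE that drives someone out is an event the protocol does collect, and subjects are told to contact the investigator about symptoms they perceive as serious. That illness drives non-attendance is plausible but not documented. Finally, all analyses are descriptive (SAP 7), and the loss is small under moderate dropout.

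All of this stands, and it narrows the point. It does not remove the gap, because the surviving provisions cover events already known or events that cause withdrawal. None provides planned detection of new events in a subject who simply cannot attend.

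**Conclusion.** The point holds in a limited form. For a subject who can no longer attend site visits, the protocol provides no status that continues SAE/pIMD follow-up, no planned detection of new events follows, and the SAP counts the subject as event-free. The resulting bias in the secondary-objective percentages is downward. Under an assumed 10–20% withdrawal, on average at mid-study, about 5–10% of events are missed if leavers have the same rate as others, and about 9–17% if they have twice the rate throughout. Both the withdrawal share and the rate ratio are assumptions. In a group of 30 with a true proportion of 20% and equal rates, the loss is about 0.3 to 0.6 of a subject with an event. This is modest and does not threaten the study, but it is cheap to avoid. The disagreement between the two definitions is a plain inconsistency and needs reconciling whatever the dropout turns out to be.

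**What to change.** Amend Protocol 9.2.1 as follows:

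- Separate (a) stopping site visits or sampling, with SAE/pIMD contact by telephone at whichever of Months 26, 32, 38, 44 and 50 remain, if the subject agrees, from (b) withdrawal of consent for all follow-up.
- Record SAEs, pIMDs and vital status at any successful contact attempt.
- Reconcile the two definitions of withdrawal. Count safety follow-up as complete if the Month 50 contact is made by visit or telephone, and keep Visit 6 as the criterion for completing immunogenicity.
- State that refusing a blood draw is not by itself withdrawal.

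In the SAP, bring the withdrawal tabulation (6.1.1) and the study-duration formula (11.1), which runs to the last visit or the discontinuation date, into line with the new status.

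The cost is a short amendment, one sentence in the consent form and a few telephone calls. The downside is that telephone reports are less detailed than those taken at a visit.

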### **9.3. Screen and baseline failures**

Screening failures are defined as subjects who are withdrawn from the study after giving informed consent, but who do not meet the inclusion and exclusion criteria.

The following information will be collected for screening failures:

- Informed consent.
- Inclusion/exclusion criteria.
- Demographic data.
- SAEs related to study participation, to concomitant use of GSK products or any fatal SAEs.
- Screening conclusion.

## **10. STATISTICAL METHODS**

### **10.1. Primary endpoint**

- Humoral immune response to the components of the NTHi Mcat investigational vaccine formulations at Month 20, Month 26, Month 32, Month 38, Month 44 and Month 50 in all subjects:
  - Anti-PD, anti-PE, anti-PilA and anti-UspA2 antibody concentrations.

### **10.2. Secondary endpoint(s)**

- Occurrence of any serious AE (SAE), during the entire study period in all subjects.
- Occurrence of any potential immune-mediated disease (pIMD) during the entire study period in all subjects.

**CONFIDENTIAL**204913 (NTHI-MCAT-006 EXT:001)  
Protocol Amendment 1 Final

### **10.3. Determination of sample size**

As this is a follow-up study, no sample size has been computed. All eligible subjects from STEP 2 of the NTHI-Mcat-001 (201281) are planned to be enrolled. Should the enrolled subjects be less than 30 in total, consideration will be given to discontinuation of the study by the Sponsor.

### **10.4. Cohorts for Analyses**

The following subject cohorts will be evaluated.

#### **10.4.1. Total vaccinated cohort**

The total vaccinated cohort (TVC) will include all subjects from STEP 2 of NTHI-Mcat-001 (201281) enrolled in this follow-up study:

- A safety analysis based on the TVC will include all subjects enrolled in this follow-up study.
- An immunogenicity analysis based on the TVC will include all subjects for whom immunogenicity data are available.

The TVC analysis will be performed per treatment administered in the parent study NTHI-Mcat-001 (201281).

#### **10.4.2. Per-protocol cohort for analysis of immunogenicity**

The per-protocol cohort for immunogenicity will consist of all subjects from the TVC who will comply with eligibility criteria, study procedures up to the last subject last visit and had immunogenicity results in the epoch.

More specifically, the Per-protocol cohort for immunogenicity will include all eligible subjects:

- Who met all eligibility criteria.
- Who did not receive a concomitant medication/ product/vaccine leading to the elimination from the Per-protocol analysis for immunogenicity (see Section [6.1.2](#)).
- Who did not present with an intercurrent medical condition leading to elimination from the Per-protocol analysis for immunogenicity (see Section [6.2](#)).
- Who complied with at least one of the immunogenicity blood sample timings as specified in [Table 5](#).
- For whom immunogenicity results are available for at least one assay in at least one of the follow-up time points.

**CONFIDENTIAL**204913 (NTHI-MCAT-006 EXT:001)  
Protocol Amendment 1 Final

## 10.5. Derived and transformed data

- **Immunogenicity**

The technical assay cut-off value is defined by the laboratory before the analysis and is described in Section [5.7.3](#).

A seronegative subject is a subject whose titre is below the cut-off value.

A seropositive subject is a subject whose titre is greater than or equal to the cut-off value.

Seroconversion is defined as the appearance of antibodies (i.e. titre greater than or equal to the cut-off value) in the serum of subjects seronegative before vaccination.

The geometric mean concentrations (GMC) are computed by taking the anti-log of the mean of the log concentration transformations. Values to be used for the antibody concentrations below the assay cut-off will be described in the Statistical Analysis Plan (SAP).

Handling of missing data: for a given subject and a given immunogenicity measurement, missing or non-evaluable measurements will not be replaced.

